1.3 Non-Clinical and Clinical Study Findings

There are no immediate benefits. In long-term, we can provide genetic risk-guided diet plans to individuals who may be at high risk.

Risks: We don't anticipate major risk since we will exclude individuals who are diabetic, pre-diabetic, have high liver fat at baseline and are at high risk for these and other metabolic diseases. The only risk can be weight gain. We will advise on cutting calories elsewhere in their daily diet. We will also advise the participants to avoid fruit juices and other sodas for the duration of 3 weeks.

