	(2) Intervention: This part is divided into two phases. Each phase entails two visits. Phase2-visit 1: The 48 enrolled (24 in each of the high and low genetic risk group) will

visit the UNC NRI clinical suite run by the Human Research Core. They will be taken to the WakeForest imaging center for their baseline MRS scan.

Visit 2: Acute fructose challenge: The next day, they will have their initial anthropometrics and Fibroscan measurements. They will then undergo an oral fructose challenge using a protocol used by Hudgins et al¹³. The participants will be provided with a drink consisting of fructose (0.75g/kg body weight) + glucose (0.45g/kg body weight) dissolved in 24 Oz of water (equal to 2 soda cans) to be consumed within 15 minutes. Blood and urine will be sampled at baseline and 1 and 3 hours after sugar drink ingestion. During the challenge period, no other beverage (except water) or food will be allowed.

3-week intervention: The 48 participants will be provided with sugar drinks for the three week period. The drinks that need to be taken per day will contain fructose (0.75g/kg body weight) + glucose (0.45g/kg body weight) dissolved in 24 Oz of water (equal to 2 soda cans) which is similar to that provided during the acute fructose challenge⁷.

[figure not shown]
Addition of glucose to fructose in the challenge and 3-week intervention induces the lipogenic effects of fructose, alleviates gastrointestinal effects of fructose and mimics the real-life situation¹⁴. They will visit at the end of each week to collect drinks for the next week. In addition, participants will be given standardized meals for the day prior to the baseline fructose challenge. They will also be instructed to avoid alcohol, juices and sodas the previous evening.

Efficacy Evaluations	Changes in liver fat accumulation through MRI scans and fibroscan measurements, and serum concentration of other lipids, liver function markers and uric acid.
Pharmacokinetic Evaluations	N/A

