3.2 Allocation to Treatment Groups and Blinding (if applicable)

- We will allocate participants to high and low genetic risk groups

3.3

Study Duration, Enrollment and Number of Subjects

- The study has three phases. First phase will have 200 participants who will visit Human Research Core clinical suite and spend about 30 minutes providing saliva sample and completing a brief questionnaire.
- Second and third phases will have 48 participants. They will first undergo a MRI scan and next day a 3 hour acute fructose challenge (total time 3.5 hours) and then will consume sugar drink as given to them. They will visit again at the end of week 3 for further biomarker, MRI scan and fibroscan measurements.

3.4

Study Population

- Inclusion criteria: Caucasian children and young adults, overweight/obese, ages between 12 and 40 years and no history of alcohol abuse (> 7 drinks per week for a year) and no history of excessive fructose intake (> 14 drinks per week for a year). We will conduct a spot glucose check using a glucometer (Accu-Chek, Roche Diagnostics, CH) to check that the glucose levels of the participants are in the normal range (fasting < 100mg/dl, post meal < 140 mg/dl and random < 200 mg/dl).
- Exclusion criteria includes ages < 12 and > 40 years, healthy weight or morbidly obese, known alcohol abuse, not of Caucasian ethnicity, pregnancy, lactation, glucose levels > 100 mg/dl if fasting, > 140mg/dl if within 2 hours post meal and > 200 mg/dl if random, baseline MRI scan of liver fat fraction > 5%²⁷, and known diagnosis of diabetes, fructose intolerance and chronic kidney disease, use of lipid or uric acid lowering medications.

4

STUDY PROCEDURES (what will be done)

4.1

Screening/Baseline Visit procedures

Phase 1: Recruitment and screening of participants:

Screening: We will recruit 200 Caucasian children and young adults fulfilling our inclusionary criteria: ages between 12 and 40 years, overweight or obese, no history of fructose intake > 14 drinks per week and alcohol abuse (> 7 drinks per week for a year). Height will be measured to the nearest 0.1 cm by a stadiometer situated against the wall in an upright standing position. Height and weight recorded will be used to calculate BMI as kg/m². We will match all participants for BMI (25kg/m² -32kg/m² or 85th-99th percentile).

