4.8 Screen failure procedures

-

5 STUDY EVALUATIONS AND MEASUREMENTS (how measurements will be made)

- At baseline and end of week 3, we will measure body weight, body composition, blood pressure, waist circumference, liver fat by transient elastography, MRI scan and serum and urinary biomarkers. Blood and urinary biomarkers will also be measured at one and 3 hour timepoints during the acute fructose challenge.
- Body weight and composition (Body weight, body fat, etc) will be measured through a body fat analyzer (Tanita Corporation of America Inc. Arlington Heights, IL)
- Waist circumference (WC) will be measured using a stretch-resistance tape at the midpoint between the lower margin of the least rib and the top of the iliac crest to the nearest 0.1 inch. Waist and hip circumferences will be measured to the nearest cm in a standing position
- Sitting blood pressure and pulse rate will be measured using the Omron digital blood pressure monitor (HEM907XL, Omron Healthcare Inc. Lake Forest, IL)

- Liver fat will be measured using MRI at the Wakeforest Imaging Center and transient elastography (Fibroscan, Echosens, Paris, FR)

Quality control: All phenotypes will be checked for distribution and accuracy of values. Phenotype data collection will be performed on the same equipment with strict quality control regulations. Assay quality is assessed by tracking coefficients of variation for quality control samples that are run with each assay. Appropriate internal standards will be used wherever necessary.

- 5.1 Efficacy Evaluation (if applicable)**
- 5.2 Pharmacokinetic Evaluation (if applicable)**
- 5.3 Safety Evaluations**

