9 SAFETY MANAGEMENT

Data and Safety monitoring plan will be instituted for the project. As per the plan, PI, co-investigators and physician will ensure that the proper protocol is being followed. Any adverse event that is reported to either the principal investigator or her designated research associates by the subject or medical staff caring for the subject and which meets the criteria will be documented as such. Any event that is reported will then generate an adverse event report, which will be submitted to the IRB. The report will include a description of the event, when and how it was reported, as well as any official chart records or documentation to corroborate the event or the

reporting of the event. All adverse events will be graded on a scale from 0 to 5. Any severe and/or unanticipated adverse event will be immediately reported to the safety officer and IRB. All other adverse events will be reported in a timely fashion to IRB, preferably within 2 weeks of the date of the event. All adverse events will be summarized annually and submitted to the IRB. The annual report will address: (1) whether adverse event rates are consistent with pre-study assumptions; (2) reason for dropouts from the study; (3) whether all participants met entry criteria; (4) whether continuation of the study is justified on the basis that additional data are needed to accomplish the stated aims of the study; and (5) conditions whereby the study might be terminated prematurely.

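### Adverse events are documented only when someone reports them, and no symptom enquiry or weight check is scheduled between baseline and the end of week 3, although participants already attend weekly

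*Combined protocol and SAP*

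**What the plan says.** **Risks.** Section 1.3 (Non-Clinical and Clinical Study Findings) states: "The only risk can be weight gain". Its control is advice to reduce calories elsewhere in the diet. The synopsis (Study Phases, Intervention) explains that glucose is added to the drink partly because it "alleviates gastrointestinal effects of fructose and mimics the real-life situation". Gastrointestinal effects do not appear in section 1.3.

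**Contacts during exposure.** The same part of the synopsis says: "They will visit at the end of each week to collect drinks for the next week". Drink collection is the only purpose given. Section 3.3 describes the next assessment after the acute challenge this way: "They will visit again at the end of week 3 for further biomarker, MRI scan and fibroscan measurements".

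**Weight.** Section 5 (Study Evaluations and Measurements) sets the times: "At baseline and end of week 3, we will measure body weight, body composition, blood pressure, waist circumference". Section 4.3 plans no follow-up after that.

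**Adverse events.** Section 9 (Safety Management), with matching text in section 10 and in the synopsis monitoring plan, starts from "Any adverse event that is reported to either the principal investigator or her designated research associates by the subject or medical staff" and adds the condition "which meets the criteria will be documented as such". The criteria are not given. Section 9 also requires grading from 0 to 5 and an annual report that addresses "whether adverse event rates are consistent with pre-study assumptions". No assumed rate is stated. The safety evaluations in the synopsis are screening and baseline checks, and section 5.3 (Safety Evaluations) is a heading without text.

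**The concern.** The plan relies on spontaneous reports to count events and then promises to judge the resulting rates. Unprompted reporting misses symptoms that participants think minor or expected. Gastrointestinal discomfort from a sugar drink is an obvious candidate, and the authors foresaw it. An undefined filter on what is documented adds a second, unknown loss.

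Two things are at stake. First, the annual comparison in section 9 would set a rate of unknown completeness against assumptions that are not written down. Second, the only control named for weight gain is dietary advice, and no weight is scheduled that would show during the 21 days whether the advice is working. The week-3 measurement comes when the drinks are finished. Participants are on site in the meantime, so the gap could be closed without new visits.

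**Working it through.** The documents give no event rate, safety sample size or safety power, so there is no figure to reproduce. The check is mainly a reading of the schedule, followed by an illustration.

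**1. Schedule during the 3 weeks**

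| Time | Contact | Safety enquiry or weight specified |
|---|---|---|
| Week 0 | MRI, then acute challenge next day | Weight yes (section 5); fixed symptom question no |
| End of week 1 | Drink collection (synopsis) | None |
| End of week 2 | Drink collection (synopsis) | None |
| End of week 3 | Biomarkers, MRI, Fibroscan, weight (sections 3.3, 5) | Weight yes; fixed symptom question no |

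Scheduled weight checks after baseline and before the end of exposure: 0. Scheduled adverse-event questions at any visit: 0. Intermediate contacts with no safety enquiry specified: 48 participants × 2 visits = 96. This counts opportunities and does not measure harm.

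**2. What the recording rule does to a rate**

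Let p be the true proportion of participants with a given symptom, and f the share of those cases that are reported and documented. The expected recorded rate is p × f, which is below p whenever f < 1. The direction is clear. The size is not, because the documents give neither p nor f.

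**3. Illustration (p and f are assumptions)**

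Expected recorded cases among all 48 = 48 × p × f:

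| p | f = 1 | f = 0.5 | f = 0.3 |
|---|---|---|---|
| 5% | 2.4 | 1.2 | 0.7 |
| 10% | 4.8 | 2.4 | 1.4 |
| 20% | 9.6 | 4.8 | 2.9 |
| 30% | 14.4 | 7.2 | 4.3 |

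Chance of recording at least one case in one genetic-risk group of 24 = 1 − (1 − p × f)^24. At p = 10%:

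- f = 1: 1 − 0.90^24 = 92%
- f = 0.5: 1 − 0.95^24 = 71%
- f = 0.3: 1 − 0.97^24 = 52%

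**4. Weight is a different case**

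Weight is measured in everyone at both ends, so no reporting share applies and the week-3 gain is not under-counted. What the schedule cannot give is any reading while the drinks are still being taken.

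**5. The two risk statements**

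Section 1.3 gives a single risk. The synopsis gives a reason for adding glucose that presupposes a second. The risk list is incomplete against the document's own text.

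**The case against.** The strongest reply is that much of this is inferred from silence. The synopsis does not say that staff ask nothing at drink collection, and participants who attend weekly can tell research staff how they feel. Sections 4.2, 4.4 and 4.5 offer a resident clinician, participants may withdraw freely, and section 9 reports reasons for dropout. A data and safety monitoring plan is to be set up and may hold the criteria and the assumed rates. Section 4.2 also plans three 24-hour diet recalls and guidance on removing about 500 kcal a day. Tolerability is not an endpoint.

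Part of this stands. But the clinician route depends on the participant coming forward, and dropout reasons catch only intolerance that leads to withdrawal. The recalls are labelled by phase with no mid-exposure timing, and they do not cover symptoms or weight. A staff habit of asking would not give comparable data unless it were written down.

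A weekly weight is also a weak signal. The 65 kg example in section 4.2 gives 65 × 1.2 = 78 g of sugar, or 312 kcal a day at an assumed 4 kcal/g, against the protocol's figure of about 500. With no compensation and an assumed 7,000 to 8,000 kcal per kg, the weekly gain would be 312 × 7 / 8,000 = 0.3 kg to 500 × 7 / 7,000 = 0.5 kg. That may not stand out from ordinary fluctuation, so the symptom questions are the more valuable part of the change.

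Several stronger readings are tempting and are not supported:

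- *Weight gain will be missed or its rate understated.* It is measured at week 3.
- *Events count only if the participant volunteers them.* Reports from treating medical staff also count.
- *Section 3.3 contradicts the weekly visits.* Section 3 is headed as a brief overview, and leaving out drink collection is not a conflict.
- *Two weights leave weight gain as an unresolvable rival explanation for a rise in liver fat.* Total weight change is available for adjustment, and its timing is not needed for that.
- *A mild stomach upset must be reported at once as unanticipated.* The synopsis shows that such effects were foreseen.
- *A wrong tolerability figure will be carried into the larger study.* The stated outputs are liver-fat and biomarker data, so this is speculation.

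**Conclusion.** The concern holds in a limited form. As written, the plan records adverse events only on report by the participant or treating staff, applies criteria it does not state, and schedules no enquiry or weight between baseline and the end of week 3. Symptom rates, gastrointestinal ones above all, are likely to be under-counted, while section 9 promises to judge event rates against assumptions that are not stated.

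The size of the under-count cannot be derived. The percentages above rest on assumed values of p and f and show only how sensitive a group of 24 is to incomplete reporting. For weight, the loss is confined to detection during exposure. The conclusion assumes that no unseen monitoring plan already provides a fixed enquiry. If one does, the protocol needs a cross-reference to it. The primary liver-fat analysis is not affected. The change is worth making because it is cheap and improves both safety information and the rates the protocol says it will use.

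**What to change.** 1. At each existing weekly drink-collection visit and at week 3, ask every participant one fixed open adverse-event question and one gastrointestinal question. Log every answer, including a negative one, whether or not it was volunteered.
2. Record weight at the same visits on the body-composition analyzer already in use.
3. State in section 9, and wherever the text is repeated, the criteria an event must meet to be documented. State the pre-study assumptions on event rates, or say that there are none.
4. Report solicited and spontaneous events separately, so that the rates can be interpreted.
5. Reconcile section 1.3 with the gastrointestinal effects acknowledged in the synopsis.

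Any action on a recorded weight or symptom is for the investigators, and none is proposed here. Extra dietary advice prompted by a weight reading would be a further intervention during exposure, so it should be recorded if given.

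Cost: a few minutes per visit, one form, equipment already on site, and more minor events to log.

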Study Objective(s)	
Our goal for this study is to generate preliminary data that is needed to support an application to NIH for funding of a larger, adequately-powered study to explore whether a set of genotypes, that increase the risk for nonalcoholic fatty liver disease (NAFLD), predispose individuals to increased de novo lipogenesis (DNL) and liver fat accumulation when exposed to fructose intake.
 
Primary Objective: To determine the impact of acute and prolonged exposure of fructose on hepatic lipid accumulation in adolescents and young adults (12-40 years) with high and low genetic risk for NAFLD using liver mass resonance imaging (MRI).
 
Secondary Objective: To explore the genetic-specific effects of fructose on markers of liver fat accumulation (fibroscan⁵ and fatty liver index⁶) and serum biomarkers related to lipids, uric acid and liver function.

Test Article(s) (If Applicable)	Sugar-Sweetened beverages
Study Design	
 a. We will screen 200 Caucasian children and young adults (12-40 years) to obtain 24 children and 24 young adults who are overweight/obese and drink <14 fructose drinks/week to participate in a 3-week fructose intervention study. The 200 participants will be genotyped for 10 SNPs involved in lipid metabolism and associated with increased NAFLD risk in previously published studies^{7,8}. We will select 12 children and young adults with 15 or more risk alleles and 12 children and 12 young adults with 6 or fewer risk alleles and provide them fructose + glucose⁹ drinks who will ingest one drink (equal to 2 soft drinks) per day for 3 weeks; b. We will measure liver fat using Liver MRI^{9,10} and transient elastography (Fibroscan)⁵ at week 0 and 3;

c. Data will be analyzed using paired and unpaired students T test to differentiate the responses between the time points and between the two groups, respectively.

Specific Aim2: Determine the impact of acute exposure of fructose on hepatic *de novo* lipogenesis

- Using the cohort described in Specific Aim1, we will conduct oral fructose tolerance test at week 0 and week 3;
- We will measure liver fat using Fibroscan
- Data will be analyzed using unpaired students T test and repeated measures ANOVA to differentiate the responses between and within the two groups, respectively.

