Specific Aim3: Determine the relationship between markers of DNL, liver fat accumulation and serum concentrations of lipids, uric acid and liver function markers before and after the fructose challenge

- We will measure serum concentrations of liver function markers, lipids and uric acid at week 0 and week 3;
- As in previous aims, data will be analyzed using students T test, and Pearsons correlations.

Subject Population	Inclusion Criteria
key criteria for Inclusion and Exclusion:	
 Subjects between 12 and 40 years No history of alcohol abuse (> 7 drinks per week) History of fructose intake of < 14 drinks per week Caucasian ethnicity BMI > 25kg/m² – 32kg/m² or 85th -99th percentile but otherwise healthy
	Exclusion Criteria
	
 ages < 12 and > 40 years Pregnant/lactating known alcohol abuse or fructose intake > 14 drinks per week not of Caucasian ethnicity glucose levels > 100 mg/dl if fasting, > 140mg/dl if within 2 hours post meal and > 200 mg/dl if random sample taking anti-hypertensive, anti-diabetic, uric acid and/or lipid-lowering medications known diagnosis of diabetes, fructose intolerance, chronic kidney disease, NAFLD or any liver-related disease, hypertriglyceridemia, polycystic ovary syndrome, hypothyroidism, obstructive sleep apnea, hypopituitarism and hypogandism BMI < 25kg/m² or > 32 kg/m² or < 85th or > 99th percentile Liver fat fraction >5% as per baseline MRI scan
Number Of Subjects	200 for first phase and 48 for the second and third phases
Study Duration	The first phase will be about 30 minutes and the second and third phase will be divided into two visits. Both visits in both phases will be about 3.5 hours each.
Study Phases	(1) Screening: We will screen participants for eligibility to participate in the study based on the inclusionary/exclusionary criteria specified above. The 200 children and young adults selected to participate will provide saliva which will be used to extract DNA and then genotype 10 SNPs. These SNPs are selected based on their association with de novo lipogenesis (DNL) or liver fat accumulation in previously published studies in Caucasians. We will select 12 children and 12 young adults with more than 15 risk alleles and 12 children and 12 young adults with less than six number of risk alleles.
Screening	
Study Treatment	
Follow-Up	

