participate and that they should consult with their primary care physician. We will also advise them on diet and lifestyle that they can follow to minimize the risk. If non-liver adverse findings are reported during MRI, we will provide the participant with a letter that they can show to their physician.

Phase 2&3- visit 2- Oral fructose challenge: After their initial anthropometrics and Fibroscan measurements, they will undergo an oral fructose challenge using a protocol used by Hudgins et al¹³. The participants will be provided with a drink consisting of 0.75g/kg fructose + 0.45g/kg glucose dissolved in 24 Oz of water to be consumed within 15 minutes. An average overweight adolescent of 65 kg will consume 48.75g (65 x 0.75g/kg) fructose and 29.25g (65 x 0.45g/kg) of glucose which is similar equivalent to the sugars in two soda cans²⁸.

Blood and urine will be sampled at baseline and 1 and 3 hours after fructose ingestion. During the challenge period, no other beverage (except water) or food will be allowed.

Anthropometric measurements: Height will be measured using a portable stadiometer. Body composition and weight will be measured by bioelectric impedance technology using the Tanita Dual Frequency total Body composition analyzer (Tanita Inc., Arlington Heights, IL). Measurements will be conducted in a standing position, with subjects wearing light clothing and without shoes. Height will be measured to the nearest 0.1 cm by a stadiometer situated against the wall in an upright standing position. Height and weight recorded will be used to calculate BMI as kg/m². Waist circumference (WC) will be measured using a stretch-resistance tape at the midpoint between the lower margin of the least rib and the top of the iliac crest to the nearest 0.1 inch. Waist and hip circumferences will be measured to the nearest cm in a standing position. Sitting blood pressure (systolic and diastolic blood pressure) will be measured three times using the Omron digital blood pressure monitor (HEM907XL, Omron Healthcare Inc, Lake Forest, IL). The means of these measurements will be used for analysis. Well trained personnel in the UNC NRI Human Research Core will administer questionnaires as well as measure anthropometrics, by one staff member to minimize measurement variation and margin of error.

Questionnaires: The following six sets of questionnaires will be administered to the study participants.

- Personal Interview Form: Information related to demographics

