- Medical History: Information related to medical conditions, procedures and surgeries
- Modifiable activity form: Information related to physical activity, sedentary time and job activities
- Medications: Information related to prescription, non-prescription and traditional medications
- Dietary data: Combination of diet recall and food frequency questionnaire will be used to obtain detailed dietary data.

Sample preparation: A total of 24 mL of blood will be drawn at fasting at baseline, 1 hour, 3 hours, at weeks 0 and 3 by a trained phlebotomist through venous puncture. After centrifugation, the serum and plasma fractions of the blood samples will be aliquoted and stored at -80°C to measure the biomarkers listed below using standard reference procedures. All samples will be labeled and inventoried as per standard protocols. Urine will be collected at the same points as blood samples collected at baseline, 3 hour at weeks 0 and 3 will be stored at -80°C. The Human Research Core will assist with phlebotomy services

Meals: All participants will be provided standardized meal for the evening prior to participation of part 1 of phase 2.

Assessment of liver fat accumulation and stiffness: Magnetic resonance imaging (MRI): We will assess liver fat accumulation at week 0 and week 3 using the 2012 Siemens MAGNETOM Skyra 3T MRI system available at the WakeForest Translational Imaging program. If the liver fat fraction >5%¹⁰ then we will exclude the participant from further participation in the nutrient challenge.

Transient elastography: We will use transient elastography to ascertain the changes in the amount of fat in the liver. Transient elastography using a **Fibroscan®** is a non-invasive method of assessing fat accumulation in liver and liver stiffness and works on the principle of vibration controlled transient elastography⁵. A vibration of mild amplitude and low frequency is transmitted through the intercostal space using a vibrator at the skin surface. The vibration induces an elastic shear that propagates through the hepatic tissue. Using pulse echo ultrasound acquisition, the velocity of the shear wave can be determined. The shear wave, directly related to tissue stiffness and expressed in kilopascal (kPa), can be a helpful aid to clinically manage patients with liver disease. The UNC Human Research Core houses a Fibroscan and its trained technicians will help with its use for this study.

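### The daily study drink largely replaces habitual fructose drinks, so the week 0 to week 3 change measures a switch from varied intake, and the analysis does not adjust for that intake

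*Combined protocol and SAP*

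**What the plan says.** **Entry.** The synopsis inclusion criterion is "History of fructose intake of < 14 drinks per week". Section 3.4 words it as "no history of excessive fructose intake (> 14 drinks per week for a year", which does not bar exactly 14. Neither place defines the size or content of a drink.

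**Study drink.** Under Study Design in the synopsis, participants "ingest one drink (equal to 2 soft drinks) per day for 3 weeks". The dose is 0.75 g/kg fructose plus 0.45 g/kg glucose. Section 4.2 gives the reference case: "An average overweight adolescent of 65 kg will consume 48.75g (65 x 0.75g/kg) fructose and 29.25g (65 x 0.45g/kg) of glucose", described as about two cans of soda.

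**Habitual drinks during the 3 weeks.** Section 1.3 states "We will also advise the participants to avoid fruit juices and other sodas for the duration of 3 weeks". Under Dietary guidance, section 4.2 adds help with removing about 500 kcal a day from the rest of the diet, with sugary drinks singled out.

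**Before baseline.** The only stated limit on sodas and juices is in the synopsis: "They will also be instructed to avoid alcohol, juices and sodas the previous evening". That evening is the one before the acute challenge. Section 3.3 puts the baseline MRI on the day before the challenge.

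**Dietary data.** Section 4.2 (Questionnaires) says "Combination of diet recall and food frequency questionnaire will be used to obtain detailed dietary data". The same section assigns frequency questionnaires and three 24-hour recalls to compliance assessment.

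**Analysis.** The synopsis plans paired t-tests over time and unpaired t-tests between risk groups. Section 6.3 plans paired t-tests and repeated measures regression of week 0 against week 3. No intake term is named. Section 4.1 matches on BMI, and the only covariate named is concomitant medication (section 4.5). Everyone receives the sugar drink, so there is no control-drink group.

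**The concern.** The synopsis states the primary objective as the effect of acute and prolonged fructose exposure on liver fat in people at high and low genetic risk. A before-and-after comparison answers that only if the step in exposure between the two scans is known and reasonably alike across participants. Here the week 0 scan reflects whatever each person usually drinks, and the week 3 scan reflects the study drink with usual sodas and juices discouraged. The step is the study drink minus what it displaced.

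Three things follow.

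- Participants whose intake barely rises pull the mean paired change towards zero.
- Differences in the step add variance to the MRI change. Section 6.4 justifies 48 participants by reduced variability and intends to size a larger study from these data. The variance carries over only to a study with the same entry and avoidance rules.
- If habitual intake differs between the risk groups, they receive different steps, and unadjusted t-tests cannot separate that from genotype.

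**Working it through.** **The plan's own figure.** 65 × 0.75 = 48.75 g fructose and 65 × 0.45 = 29.25 g glucose. Both reproduce exactly.

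**Inputs**
- Fructose per soda implied by section 4.2: 48.75 / 2 = 24.375 g.
- Study drink in soda equivalents at 65 kg: 2 per day × 7 = 14 per week.
- Habitual intake D: 0 to 13 drinks per week (synopsis).
- Assumptions: all habitual drinks are displaced (full adherence), each holds 24.375 g, and one study drink is taken per day.

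**Formulas**, with W the weight in kg:
- Net change (g/day) = 0.75 × W − D × 24.375 / 7
- Break-even weight (kg) = (D × 24.375 / 7) / 0.75

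| D per week | Displaced, g/day | Net at 65 kg, g/day | Break-even weight, kg |
|---|---|---|---|
| 0 | 0 | +48.8 | none |
| 7 | 24.4 | +24.4 | 32.5 |
| 10 | 34.8 | +13.9 | 46.4 |
| 13 | 45.3 | +3.5 | 60.4 |

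**Lower weights at 13 per week.** At 50 kg: 37.5 − 45.3 = −7.8 g/day. At 45 kg: 33.75 − 45.3 = −11.5 g/day. The sign can change because the dose scales with weight and a soda does not.

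**Who could be below break-even.** At the adult BMI floor of 25 kg/m², 60.4 kg corresponds to a height of √(60.4 / 25) = 1.55 m. Adolescents enter by BMI percentile, so they are the likelier group.

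**Sensitivity to the undefined drink** (assumed 18 to 30 g fructose), at 13 per week:
- 18 g: displaced 13 × 18 / 7 = 33.4 g/day; break-even 44.6 kg; net at 65 kg +15.3 g/day.
- 30 g: displaced 13 × 30 / 7 = 55.7 g/day; break-even 74.3 kg; net at 65 kg −7.0 g/day.

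**Sensitivity to weight.** The largest-to-smallest ratio is 48.75 / 3.48 = 14 at 65 kg. At an illustrative 85 kg it is 63.75 / 18.48 = 3.4. The ratio is unstable because its denominator is near zero at 65 kg; the range in g/day is the better summary.

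**Chance imbalance, illustration only.** If D were uniform on the whole numbers 0 to 13 (an assumption), its SD is 4.03, and the mean net rise at 65 kg is 14 − 6.5 = 7.5 soda equivalents per week. With 24 per risk group the standard error of the difference in mean habitual intake is 4.03 × √(2/24) = 1.16. The 95% chance range is then ±1.96 × 1.16 = ±2.3 drinks per week. With 12 per cell it is ±3.2.

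**Dependence on one drink a day.** The synopsis and sections 1.2 and 7 specify one study drink daily. Section 4.2 (Medical care) refers to three sugar drinks a day. At three study drinks a day, break-even at 13 per week would be 60.4 / 3 = 20 kg, and no fall would be plausible. The passages must be reconciled.

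**The case against.** The strongest reply is that the assigned dose is the same per kg for everyone and that the avoidance advice standardises background intake during the intervention. Without it, total intake would vary more. That is correct: the level during the 3 weeks is fairly common, and what varies is the increment. But a week 0 to week 3 change responds to the increment.

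A reader might infer that some participants' fructose intake actually falls. The documents do not support that as fact. At 65 kg and the implied soda content, even 13 drinks a week leaves a small rise. A fall needs near-cap intake, low weight and full adherence together, or larger drinks, and the documents give no distribution of weight or intake.

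A reader might also infer that participants must stop their usual drinks. Sections 1.3 and 4.2 offer advice and guidance, so the figures above are the full-adherence case. Partial adherence would not make the increment uniform; it would make it less predictable.

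A further tempting reading is that the genotype contrast is biased. Nothing in the documents suggests that habitual intake differs by allele count. If it is balanced, the cost is dilution and noise, in a study that calls itself exploratory and concedes limited power.

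Finally, the repeated measures regression could carry an intake covariate, and the dietary data do have a stated use. Both are true, but no such covariate is specified, and the stated use is compliance.

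**Conclusion.** The point holds in this form: the week 0 to week 3 change estimates a switch from varied habitual intake to the study drink, not the effect of adding 0.75 g/kg/day, and no planned analysis accounts for the variation. Under full adherence and 24.4 g per soda, the net rise at 65 kg spans about +49 to +3.5 g/day. A negative change is possible only for near-cap drinkers under about 60 kg, and that threshold moves between about 45 and 74 kg with the assumed drink content. Dilution and added noise follow from the design. Bias between risk groups is conditional on a difference in habitual intake, which can arise by chance with groups of 24. All of this rests on one study drink a day.

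**What to change.** 1. Derive baseline habitual fructose intake (g/day) for each participant from the food frequency questionnaire and recall taken before the first study drink. Define what counts as a drink.
2. Prespecify that variable as the covariate in a linear regression of MRI liver-fat change on genetic risk group, in place of the unadjusted unpaired t-test. Use baseline intake alone: net change mixes in body weight through the per-kg dose and behaviour after baseline, so it should not be the adjustment variable.
3. Tabulate baseline intake and net change by risk group, as description only.
4. Word the 3-week result as a change from habitual intake.
5. Reconcile the reference to three sugar drinks a day in section 4.2 with the one per day in the synopsis and sections 1.2 and 7.

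The cost is one derived variable, one degree of freedom (residual 46 to 45 in a two-group model of 48) and some rewording, with no new visits or measurements. Error in questionnaire and recall data makes the adjustment partial, and the stated exposure contrast will look smaller than the nominal dose.
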